4.2 EXCLUSION CRITERIA

Subjects meeting any of the following exclusion criteria at Screening will not be enrolled in the

study:

1. Presence of serious illness, medical condition, or other medical history, involving the heart, kidney, liver, or other organ system, including abnormal laboratory parameters, which, in the opinion of the Investigator, would be likely to interfere with a subject's participation in the study or with the interpretation of the results.
2. Have known active central nervous system disease or active, uncontrolled, clinically significant infection(s)
3. Have other active malignancies or other malignancies within 12 months before enrollment, except non-melanoma skin cancer or cervical intraepithelial neoplasia
4. Are receiving any other investigational therapy or protocol-prohibited therapy
5. Have received previous treatment with tosedostat
6. Pregnant or breastfeeding females
7. Any prior or co-existing medical condition that in the Investigator's judgment will substantially increase the risk associated with the subject's participation in the study
8. Psychiatric disorders or altered mental status precluding understanding of the informed consent process and/or completion of the necessary study procedures
9. Significant* cardiovascular disease defined as:
 - a. Active heart disease including myocardial infarction within 6 months prior to study entry
 - b. Symptomatic coronary artery disease
 - c. Uncontrolled or clinically significant arrhythmia, angina, congestive heart failure
 - d. Presence of clinically significant valvular heart disease
 - e. Presence of clinically significant conduction defect on screening ECG
 - f. Uncontrolled hypertension (i.e., systolic BP >160mmHg, diastolic >90 mmHg in repeated measurements) despite adequate therapy
 - g. Clinically significant atrial fibrillation
10. LVEF ≤ 50%
11. Baseline troponin I and b-type natriuretic peptide > Grade I

* Grade 3/4 in the CTCAE v4.0 grading would generally be considered clinically significant, although this remains a judgment for the Investigator to make.

12. Prior exposure cardiotoxic agent, such as anthracycline, within 3 months of enrollment
13. Concomitant use of drugs that prolong QT/QTc interval except antibiotics, antifungals, and other antimicrobials used as standard of care for the treatment and prevention of infection and/or other such drugs clinically indicated for patient care. When use of concomitant medications with QT-prolonging potential is necessary, ECG must be repeated 4 hours post-dose on Day 1 (+1 day), on Day 3 (± 1 day), and on Day 7 (± 1 day), and as clinically indicated, relative to start of agent with QT-prolonging potential. QTc will be calculated using the Fridericia formula. For subsequent use of same concomitant medication, ECG may not be repeated if it did not cause QTc prolongation with tosedostat.
14. Gastrointestinal disorders that may interfere with absorption of drug
15. Active serious infection or sepsis
16. Clinically significant interstitial lung disease

4.3 DURATION OF CLINICAL STUDY

Enrollment in this clinical study is expected to be completed in approximately 24 months, and the total study duration, including the 30-day follow up period, will be approximately 36-48 months. Patients have up to 4 cycles of treatment to achieve a response to tosedostat; responding patients may continue treatment indefinitely, at the discretion of the treating investigator, in collaboration with the sponsor.

5 STUDY ASSESSMENTS

Each treatment cycle consists of 28 days. Visits have a ± 2 -day visit window. Day 28 visits may be combined with day 1 visits of subsequent visits to reduce the travel burden of patients.

5.1 SCREEN PERIOD ASSESSMENT (Study Days -28 to 1)

Initiate and complete all screening activities within 14 days before Day 1 of study. Screening tests may be repeated if minor or transient abnormalities are found in lab values or vital signs. The following assessments will be performed:

- Obtaining and signing informed consent
- Review of inclusion and exclusion criteria
- Recording of subject demographics
- Recording of relevant medical history, to record all relevant past and present medical and surgical conditions, diseases or events including allergies or transplants. Recording should also include prior malignancies (whether primary/secondary MDS and other relevant etiology) and its previous treatment (including chemotherapy regimens and doses)
- Physical examination, including assessment of extramedullary disease
- Recording of ECOG performance status
- Vital signs, including body temperature ($^{\circ}\text{C}$), pulse rate and systolic and diastolic blood

- pressures, height (cm), weight (kg), and body surface area
- Determination of LVEF by echocardiography (ECHO)
- Perform 12-lead ECG
- Collect blood samples for hematology, chemistry, cardiovascular panel (including troponin I, b-type natriuretic peptide), coagulation
- Collect Urinalysis
- Recording of concomitant medications and concomitant significant non-drug therapies, including blood product transfusions
- Bone marrow aspirate and biopsy for assessment of bone marrow morphology, cytogenetics, flow cytometry, and immunophenotyping

Once the patient meets the inclusion and exclusion criteria, a request for registration must be sent. Patients will be registered with the Weill Cornell Medical College (WCMC) Joint Clinical Trials Office (JCTO). To register a patient, email the following documents to the regulatory assistant and regulatory coordinator:

- WCMC Patient registration form
- First and last page of the fully executed informed consent form, plus additional pages if checkboxes for correlative studies are required.
- Fully executed short form, if applicable
- Fully executed HIPAA research authorization form
- Eligibility checklist signed and dated by investigator and research nurse/study coordinator
- Documentation of any eligibility waivers granted
- Source documentation to confirm eligibility
- For inpatients, signed consent documentation template (WCMC only)

Documentation of patient registration will be faxed to the Investigational Pharmacy to allow for release of study agent. Patient is eligible to begin treatment once a confirmation email has been sent to study team.

5.2 TREATMENT PERIOD ASSESSMENTS

5.2.1 Cycle 1

Study visits have a [± 2-day visit window](#)

5.2.1.1 Day 1 (Baseline)

If subjects meet all inclusion and exclusion criteria, they will return to the Investigational site within 28 days after the Screening Visit and the following assessments will be performed:

- Review of any changes since the Screening Visit which may affect inclusion/exclusion criteria
- Recording of any changes to medical history since the Screening Visit
- Recording of baseline signs and symptoms
- Physical examination
- Assessment of ECOG performance status

- Vital signs, including body temperature (°C), pulse rate and systolic and diastolic blood pressures, weight (kg), and body surface area
- Collect blood samples for hematology, troponin I, b type natriuretic peptide, coagulation, and blood chemistry (may be omitted if obtained within 7 days as part of the screening visit)
- Collect urinalysis (may be omitted if obtained within 7 days as part of the screening visit)
- Perform 12-lead ECG
- Recording of concomitant medications and significant non-drug therapies including blood product transfusions
- Assess and record of AEs
- Dispense tosedostat
- Instruct subjects on satisfactory completion of treatment diary

5.2.1.2 *Days 8, 15, 22*

- Physical examination
- Vital signs, including body temperature (°C), pulse rate and systolic and diastolic blood pressures, weight, and body surface area
- Collect blood samples for hematology, chemistry, troponin I, b-type natriuretic peptide
- Perform 12-lead ECG
- Recording of concomitant medications and significant non-drug therapies including blood product transfusions
- Recording of AEs

5.2.1.3 *Days 28*

- Physical examination
- Vital signs, including body temperature (°C), pulse rate and systolic and diastolic blood pressures, weight, and body surface area
- Collect blood samples for hematology, chemistry, troponin I, b-type natriuretic peptide
- Perform 12-lead ECG
- Transthoracic echocardiogram
- Recording of concomitant medications and significant non-drug therapies including blood product transfusions
- Recording of AEs

5.2.2 *Cycles 2*

Patients with a documented response of CR, PR, hematologic improvement or stable disease at the end of Cycle 2 may be eligible to continue treatment indefinitely with tosedostat, at the discretion of the Investigator.. Study visits during Cycles 2+ have a 2-day window. Patients must have returned to at least baseline hematological parameters at the start of each cycles unless investigator deems cytopenias are secondary to underlying disease, and all drug-related non-hematological toxicities must have resolved to < grade 2.

5.2.2.1 *Day 1*

- Recording of any changes to medical history since the Screening Visit

- Recording of baseline signs and symptoms
- Physical examination, including assessment of extramedullary disease
- Assessment of ECOG performance status
- Vital signs, including body temperature (°C), pulse rate and systolic and diastolic blood pressures, weight (kg), and body surface area
- Collect blood samples for hematology, troponin I, b type natriuretic peptide, coagulation, and blood chemistry (blood samples may be omitted if obtained within 7 days)
- Collect urinalysis (may be omitted if obtained within 7 days)
- Perform 12-lead ECG
- Transthoracic echocardiogram, only if patient has been off of tosedostat for more than 2 weeks since prior cycle
- Recording of concomitant medications and significant non-drug therapies including blood product transfusions
- Assess and record of AEs
- Examination of subject treatment diary and return of unused tosedostat
- Dispense tosedostat

5.2.2.2 *Days 8, 15, 22*

- Physical examination, including assessment of extramedullary disease
- Vital signs, including body temperature (°C), pulse rate and systolic and diastolic blood pressures, weight, and body surface area
- Collect blood samples for hematology, chemistry, troponin I, b-type natriuretic peptide
- Perform 12-lead ECG
- Recording of concomitant medications and significant non-drug therapies including blood product transfusions
- Recording of AEs

5.2.2.3 *Days 28*

- Physical examination, including assessment of extramedullary disease
- Vital signs, including body temperature (°C), pulse rate and systolic and diastolic blood pressures, weight, and body surface area
- Collect blood samples for hematology, chemistry, troponin I, b-type natriuretic peptide
- Perform 12-lead ECG
- Transthoracic echocardiogram
- Recording of concomitant medications and significant non-drug therapies including blood product transfusions
- Recording of AEs

5.2.3 Even Cycles Day 28

Response to be assessed through examination of bone marrow and peripheral blood according to the 2006 IWG criteria.²⁰

- Collect samples for local laboratory evaluation for hematology
- Bone marrow aspiration and/or biopsy for confirmation of response
- Record concomitant medications
- Assess and record AEs

Patients with noted responses of CR or PR must have their responses confirmed 4 weeks after initial documentation of response. Patients with noted responses of hematologic improvement at the end of Cycle 2 must have their responses confirmed 8 weeks after initial documentation of response.

5.3 END-OF-TREATMENT SAFETY EVALUATION VISIT

Patients will have an End-of-Treatment Safety Evaluation Visit at discontinuation of tosedostat treatment and before the start of a new cancer therapy. Ideally, the End-of-Treatment Visit occurs on the day the decision to discontinue study treatment is made, but should be within 7 days of discontinuation of tosedostat.

If a patient is lost to follow up and does not complete the End-of-Treatment Visit per protocol, the investigator reports any known AEs that occurred up to last study visit. If at the End-of-Treatment Visit a patient is experiencing ongoing AEs assessed as possibly related to tosedostat, follow up the events until each related AE has returned to baseline, has stabilized and is considered irreversible, or the patient has died.

Complete the following at the End-of-Treatment Safety Evaluation Visit:

- Update concomitant medications
- Perform complete physical examination and weight
- Assess ECOG performance status
- Perform a 12-lead ECG
- Transthoracic echocardiogram
- Measure and record vital signs
- Collect samples for hematology and serum chemistry
- Collect BM biopsy or aspirate (if clinically indicated) for patients who have relapsed
- Assess and record AEs

5.4 UNSCHEDULED VISITS

An unscheduled visit may be performed for a variety of reasons, including confirmation of bone marrow or hematologic responses, safety investigations, additional treatments such as transfusions, and case reviews. Where an unscheduled visit is performed for safety reasons, the Investigator should consider performing appropriate investigations from those listed below. Appropriate investigations for a CR/PR confirmation visit should include:

- Hematology sample
- Bone marrow aspirate and biopsy for assessment of morphology, cytogenetics, flow cytometry

Appropriate investigations in other circumstances may include:

- Physical examination, including assessment of extramedullary disease, height, weight,

and body surface area

- Vital signs, including body temperature (°C), pulse rate and systolic and diastolic blood pressures
- Blood samples for hematology, troponin I, b-type natriuretic peptide, chemistry
- Urinalysis
- Cardiovascular panel and LVEF assessment (ONLY if the unscheduled visit is for a possible cardiovascular AE)
- Recording of concomitant medications and concomitant significant non-drug therapies including blood product transfusions
- Recording of AEs
- Bone marrow aspiration and biopsy

5.5 SUBJECT FOLLOW-UP

Survival data for subjects who complete the study or withdraw from the study will be collected every 3 months and recorded until the time of death or the subject is lost to follow-up. LVEF assessment by transthoracic echocardiogram as well as electrocardiogram will be done every 12-24 weeks after study discontinuation or through study completion if possible for those subjects who experience at least a grade II decrease of ejection fraction at end of treatment. Adverse events must be recorded for 28 days after last dose of study drug. All adverse events must be followed until resolution as outlined in Section 7.3.6.5.

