3.1.4 Clinical Study Endpoints

The primary endpoint the study is to evaluate the safety and efficacy of tosedostat in patients with myelodysplastic syndrome who have relapsed after or are refractory or intolerant to azacitidine or decitabine. The primary endpoint for patients is overall survival.

The following secondary endpoints will be evaluated:

- Hematological improvements (erythroid response [ER], platelet response [PLR] and neutrophil response [NR]) according to 2006 IWG criteria (Appendix 2), including reduction in RBC and/or PLT transfusion needs
- Overall response (complete remission [CR], partial remission [PR], bone marrow complete response [BMCR], and stable disease [SD] according to 2006 International Working Group (IWG) criteria, including, among responders, the distribution of time to response and the duration of response (Appendix 2). All responses of CR must be confirmed 4 weeks after achievement.
- Improvements of cytogenetics as evaluated by the change in aneuploidy in BM according to 2006 IWG criteria
- Safety and tolerability of tosedostat

- Time to AML transformation

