5.7.4 Criteria for Protocol-Defined Required Discontinuation of Treatment

- Discontinue treatment with tosedostat if patients experience any of the following:
- Do not achieve CR, PR, hematologic improvement, or bone marrow remission after four cycles of treatment with tosedostat alone or 4 cycles of azacitidine if azacitidine is added to tosedostat.
- Experience disease progression
- Develop an intercurrent illness that prevents further treatment with tosedostat
- Develop unacceptable/intolerable AE(s)
- Withdraw from the clinical study
- Become pregnant
- Receive other systemic cancer therapy or protocol-prohibited medications
- Have general or specific changes that render the patient unsuitable for further treatment with tosedostat, in the judgment of the Investigator

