6.6 PRIOR AND CONCOMITANT TREATMENTS

Medications taken by, or administered to, the subject within 28 days prior to first dose of tosedostat, or up to 28 days after the final dose of tosedostat, should be recorded. The entry should include the generic name, dose regimen, route, indication, and dates of use.

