11 APPENDIX

11.1 APPENDIX 1: SCHEDULE OF ASSESSMENTS

Assessment	Screening Day -14 to 1	Baseline Cycle 1 Day 1	Cycle 1 Day 8, 15, and 22	Cycle 1 Day 28	Cycle 2+ Day 1	Cycle 2+ Day 8, 15, and 22	Cycle 2+ Day 28	End of Treatment Safety Evaluation Visit ⁵
Obtain informed	X							
Record subject demographics	X							
Review inclusion/exclusion criteria	X	X						
Medical history ¹	X	X						
Baseline signs and symptoms		X						
Physical examination	X	X	X	X	X	X	X	X
ECOG performance	X	X			X		X	X
Vital signs ²	X	X	X	X	X	X	X	X
Hematology including blood film	X	X ³	X	X	X	X	X	X
Troponin I & b-type natriuretic peptide	X	X			X			X
Coagulation	X	X ³			X		X	X
Blood chemistry	X	X ³	X	X	X	X	X	X
Urinalysis	X	X ³		X	X		X	X
ECG	X	X	X	X	X	X	X	X
LVEF ⁶	X			X	X ⁷		X	X
Concomitant medication/non-drug therapies	X	X	X	X	X	X	X	X
Bone marrow aspiration or biopsy	X						X ⁴	X
Research studies (bone marrow and peripheral blood collection) ⁸	X		X				X	
Adverse events		X	X	X	X	X	X	X
Administer/Dispense tosedostat		X			X			
Review treatment Diary/Return of tosedostat								X

1. Including leukemia history, previous therapy, and pre-existing diseases; new symptoms and signs occurring between screening and baseline will be recorded as medical history if completed, baseline symptoms and signs if ongoing and blood product transfusion history
2. Vital signs will include height, weight, body surface area, body temperature (°C), pulse rate, systolic and diastolic blood pressures

3. Hematology, blood chemistry, and urinalysis may be omitted if screening visit within 7 days
4. Bone marrow samples will be collected on even cycles on days 28 for response. Bone marrow biopsy has ± 10 day window
5. End of Treatment Safety Evaluation Visit (Follow-up) will be 28 (+2 day window is allowed) days after last dose of study drug or before start of new anticancer therapy.
6. LVEF evaluation via transthoracic echocardiogram
7. Transthoracic echocardiogram on day 1 if patient has been off of tosedostat for more than 2 weeks since prior cycle.
8. Bone marrow aspirate and peripheral blood will be collect at baseline, week 2 during cycle 1 (blood only), the end of cycle 2, and during other clinically relevant time points deemed safe by the investigator

Note: Day 28 visits and day 1 visits of subsequent cycles may be combined to reduce travel burden on patients

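### No AML status, off-treatment relapse or subsequent therapy is scheduled for collection after treatment ends, so time to AML transformation is cut off at an informative stopping point

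*Combined protocol and SAP*

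**What the plan says.** Section 3.1.4 lists "Time to AML transformation" and, among responders, duration of response as secondary endpoints. Section 5.2.3 and Appendix 1 schedule marrow-based response assessment on Day 28 of even cycles. The Appendix 1 schedule ends with the end-of-treatment visit.

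After treatment, the plan provides for the following:

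- Section 5.5, all subjects: "Survival data for subjects who complete the study or withdraw from the study will be collected every 3 months", until death or loss to follow-up.
- Section 5.5, safety: "Adverse events must be recorded for 28 days after last dose of study drug", with follow-up to resolution.
- Section 5.5, subjects with at least a grade II fall in ejection fraction at end of treatment: "LVEF assessment by transthoracic echocardiogram as well as electrocardiogram will be done every 12-24 weeks after study discontinuation".
- Section 6.6: medications taken "up to 28 days after the final dose of tosedostat, should be recorded".
- Section 3.1.3: 30 days of follow-up after the End-of-Treatment Visit.

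Section 5.7.4 requires treatment to stop at progression, at unacceptable toxicity, and for patients who "Do not achieve CR, PR, hematologic improvement, or bone marrow remission after four cycles of treatment with tosedostat alone", or after four cycles of azacitidine where it has been added. Section 8 gives no censoring or competing-risk rule for either secondary endpoint.

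On the end-of-treatment marrow, Section 5.3 says "Collect BM biopsy or aspirate (if clinically indicated) for patients who have relapsed". In the Appendix 1 row "Bone marrow aspiration or biopsy", the end-of-treatment cell is marked without any qualifier; footnote 4 belongs to the Cycle 2+ Day 28 cell. Sections 5.3 and 5.7.5 place the visit within 7 days of stopping. Appendix 1 footnote 5 places it 28 (+2) days after the last dose, or before new anticancer therapy.

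**The concern.** A patient without a qualifying response leaves treatment after four cycles, or earlier for toxicity, and remains at risk of AML. If AML is diagnosed at month 6, the site is in contact every 3 months, but nothing in the plan asks for the diagnosis or its date. The same applies to a responder who stops for toxicity and relapses later, and to a patient who starts a new therapy or has a transplant more than 28 days after the last dose.

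Patients who stop are unlikely to have the same AML risk as those who stay on, because stopping follows non-response, progression or toxicity. Censoring at treatment stop would therefore be informative. Counting stopped patients as AML-free until death or last contact would be worse. Either way, transformation is under-counted, and Section 8 does not say which approach applies. Without later-therapy dates, overall survival cannot be described by what patients received next.

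**Working it through.** **The plan's own figure.** The plan gives no figure on this point. Its one design calculation is power for median survival of 6 versus 9 months (Section 8: 80 patients, one-sided 10%, at least 85%). It reproduces as a one-sample comparison of the proportion alive at 6 months. With p0 = 0.50 and p1 = 0.5^(6/9) = 0.630, z = [(0.630 - 0.500)√80 - 1.2816 × 0.5] / √(0.630 × 0.370) = 1.08, giving 86.0%. Nothing below changes it.

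**Transformations after treatment stop.** Inputs:

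- Survival medians m = 6 and 9 months, exponential (Section 8); λ = ln2/m = 0.1155 and 0.0770 per month.
- One third of patients transform (Section 1, which describes MDS in general; assumed to apply here).
- Stop after four cycles, 112 days = 112/30.4375 = 3.68 months (Section 5.7.4). With azacitidine added after cycle 2 (Section 6.3), stop after 2 + 4 = 6 cycles, 168 days = 5.52 months.

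Assume a constant transformation hazard of λ/2 alongside a death hazard of λ. The share transforming before death is then 0.5λ/1.5λ = 1/3, as required. Among those who transform, the time to transformation is exponential with rate 1.5λ, so the share falling after a stop at c months is exp(-1.5λc).

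| Stop | m = 6 | m = 9 |
|---|---|---|
| 4 cycles, c = 3.68 | exp(-0.638) = 53% | exp(-0.425) = 65% |
| 6 cycles, c = 5.52 | exp(-0.957) = 38% | exp(-0.638) = 53% |

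If every transformation in the 28 days after the last dose were picked up through adverse-event reporting, c becomes 140 or 196 days (4.60 or 6.44 months). The shares fall to 45% and 59% (four cycles) and 33% and 48% (six cycles).

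All these figures describe patients who stop at the cap. Patients who stop earlier for toxicity raise the share; in OPAL, 9 of 38 on 120 mg (24%) stopped for drug-related toxicity (Section 1.1.4.3). Patients who stay on longer lower it.

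**Patients affected.** If nobody stays past the cap, the number of 80 still alive once the 28-day window closes is 80·exp(-λc). That is 47 (m = 6) or 56 (m = 9) with the four-cycle cap, and 38 or 49 with the six-cycle cap.

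**Share of follow-up time.** With follow-up truncated at 30 months, the share of survival time beyond the cap plus 28 days is [exp(-λc) - exp(-30λ)] / [1 - exp(-30λ)]. At m = 9 this is 67% (four cycles) or 57% (six cycles) if nobody stays longer. A simulation with 10-50% of patients staying on for a further median of 3 to 12 months (assumed) and survival medians of 6 to 12 months gives 30-70%.

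**Duration of response.** Sections 4.3 and 5.2.2 let responders continue indefinitely, marrow is repeated on even cycles, and Section 5.7.4 ends treatment at progression. A relapse that ends treatment is therefore seen on study. The date is lost only when a responder stops for toxicity, intercurrent illness, withdrawal or other therapy. The documents do not allow that subset to be sized.

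**The case against.** The best opposing case is that the gap is inferred from silence.

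- Section 7.4 says REDCap will hold all treatment, toxicity and efficacy data, and the form fields are not shown. This is a general statement and schedules no assessment or question after treatment.
- Survival data is not defined, and the Survival row of Appendix 2 includes event-free, progression-free and disease-free survival. That row does not list AML transformation or next therapy, and no off-treatment assessment would supply the disease-based endpoints.
- Section 5.4 permits unscheduled visits with marrow, but does not require them.
- Adverse-event reporting could catch AML. New events are recorded for only 28 days after the last dose; after that, Section 7.3.6.5 asks only for serious events judged related to tosedostat.

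Other parts of the objection stand, and they limit what a reader might infer:

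- That survival alone is collected. Adverse events, 28 days of medications and cardiac tests in a subset are collected too, though none of these measures disease status.
- That duration of response is generally unobserved. It is mostly observed, for the reason shown above.
- That 53-65% is a floor. The azacitidine path lowers it to 38-53%. Section 5.2.2 also lets stable disease continue indefinitely, which conflicts with Section 5.7.4; those passages must be reconciled.
- That missing next-therapy dates are what prevents attributing survival to tosedostat. That limit comes mainly from the single-arm comparison with a historical 6-month median; the dates would help describe survival only.
- That the marrow mismatch costs the last disease assessment. A patient stopped under the four-cycle rule already has a scheduled Cycle 4 Day 28 marrow.

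**Conclusion.** The point holds for time to AML transformation and for subsequent therapy. As written, the plan schedules neither after the end-of-treatment visit and the 28-30 day window, and the reasons for stopping make the truncation informative. Its illustrative size is 53-65% of transformations after a four-cycle stop and 38-53% after a six-cycle stop. This rests on exponential survival with a median of 6 to 9 months, a constant transformation hazard, and a one-third transformation rate borrowed from MDS in general. Transformations that present as progression end treatment and are seen, which a constant hazard does not reflect, so the percentages give scale and are not predictions. A claim that most follow-up time is unobserved is not secure, because the share runs from 30% to 70% across plausible assumptions.

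For duration of response, the loss is confined to responders who stop for a reason other than progression. Overall survival itself is followed to death or loss to follow-up under Section 5.5, and the power calculation is unaffected. The conflict over the end-of-treatment marrow and visit timing is a separate, smaller documentation fault. The change is cheap and should be made.

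**What to change.** In Section 5.5, add to the 3-monthly contact, from routine records and with no study-mandated marrow:

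1. AML diagnosis: yes/no, date and basis.
2. Date of relapse or progression, for patients who stopped while in response.
3. First subsequent anticancer therapy or transplant: type and date.

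In Section 8, define time to AML transformation regardless of treatment stop, with death as a competing event. Analyse duration of response on the same extended data, state the censoring rules for both, and use the next-therapy data to describe overall survival, not to attribute it.

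Reconcile Section 5.3 with Appendix 1 on who has the end-of-treatment marrow, and Sections 5.3 and 5.7.5 with Appendix 1 footnote 5 on when the visit takes place. Because the added fields rely on the long-term contact, Section 3.1.3 (30 days of follow-up) and Section 5.6 (trial ends at the last end-of-treatment visit) should also be squared with Section 5.5.

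The cost is a few fields on an existing contact and a short amendment, with no extra visits. The downside is that off-treatment dates from routine care are less exact than those from scheduled assessments.

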3.1.3 Follow-up

After completion of the End-of-Treatment Visit, all patients are followed up for 30 days.

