5.7.5 Follow Up at Treatment Discontinuation or Early Withdrawal

Patients treated with tosedostat should have an End-of-Treatment Visit within 7 days of last dose of tosedostat and before the start of a new cancer therapy. End-of-Treatment Visit assessments are listed in Section 5.3.

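### Time to AML transformation is a secondary endpoint, but no section asks for AML status once post-treatment contact is survival only, so the end of planned AML observation depends on response

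*Combined protocol and SAP*

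**What the plan says.** The secondary endpoint "Time to AML transformation" appears in the synopsis, Section 2 and Section 3.1.4, without a definition of transformation.

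**During treatment.** Marrow is examined at screening and then at response assessments: "Bone marrow samples will be collected on even cycles on days 28 for response" (Appendix 1, footnote 4).

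**At end of treatment.** Appendix 1 marks a marrow at this visit, whereas Section 5.3 asks for less: "Collect BM biopsy or aspirate (if clinically indicated) for patients who have relapsed". The timing also differs. Under Section 5.7.5 patients "should have an End-of-Treatment Visit within 7 days of last dose of tosedostat", while Appendix 1 footnote 5 puts the visit 28 days (+2) after the last dose.

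**After treatment.** Section 3.1.3: "After completion of the End-of-Treatment Visit, all patients are followed up for 30 days", with no content specified. Section 5.5: "Survival data for subjects who complete the study or withdraw from the study will be collected every 3 months", until death or loss to follow-up. Section 5.5 also asks for LVEF and ECG in patients with an ejection-fraction decrease, and for adverse events to 28 days after the last dose.

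**Who stops.** Section 5.7.4 requires discontinuation at progression and for patients who "Do not achieve CR, PR, hematologic improvement, or bone marrow remission after four cycles of treatment with tosedostat alone", or after four cycles of azacitidine if it is added. By contrast, "responding patients may continue treatment indefinitely" (Section 4.3).

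**Analysis.** Section 8 names Kaplan-Meier for overall survival. It gives no definition, censoring rule, competing-event rule or method for time to AML.

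**The concern.** An event that nobody is asked to record after treatment can be analysed only for the period in which it would have been seen. Here that period ends for reasons tied to the disease. Non-responders leave after four cycles. Progressors leave at progression, which Appendix 2 allows on cytopenia, a haemoglobin fall, transfusion dependence, or a blast rise well short of AML (for example from 5-10% to above 10%). Later AML follow-up then comes mainly from responders.

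The natural analysis of such data would censor stopped patients near treatment stop and let those still treated stand in for them. That is valid only if the two groups have the same future course. If they differ, a named secondary endpoint is biased, and the dates needed to correct it may not be recoverable later.

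**Working it through.** The plan states no figure for this endpoint, so there is none to reproduce. The check has three steps.

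**1. When planned contact other than for survival ends**

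Inputs: 28-day cycles (Section 5); stop after four cycles without response (5.7.4); visit within 7 days of last dose (5.3, 5.7.5) or at 28 + 2 days (Appendix 1 footnote 5); 30 days after that visit (3.1.3).

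- Tosedostat alone: stop at 4 × 28 = day 112. End at 112 + 7 + 30 = day 149, or 112 + 30 + 30 = day 172.
- Azacitidine in Cycles 3 to 6: stop at 6 × 28 = day 168. End at 168 + 37 = day 205, or 168 + 60 = day 228.

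Permitted interruptions and delayed cycle starts could move these days later.

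**2. How many patients are alive then**

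Section 8 plans with exponential survival, a median M of 6 months, an anticipated median of at least 9, and 80 patients. Alive at t = 0.5^(t/M), with 30.44 days per month.

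| Day | Months | M = 6 | M = 9 |
|---|---|---|---|
| 112 | 3.68 | 65.4% (52 of 80) | 75.3% (60) |
| 149 | 4.90 | 56.8% (45) | 68.6% (55) |
| 172 | 5.65 | 52.1% (42) | 64.7% (52) |
| 205 | 6.74 | 45.9% (37) | 59.5% (48) |

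These are all patients, including responders still observed and any already transformed.

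**3. Illustration of the bias (hazards and shares assumed)**

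The documents give no AML rate or response rate for this population. Take patients alive and AML-free at day 112 and follow them to month 12, so T = 12 − 3.68 = 8.32 months. A share s (25-50%) has stopped. The AML hazard is h (0.02-0.05 per month) in those still treated and HR × h (HR 1 to 3) in those stopped. The death hazard is d = ln2/M in both groups.

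- G(a, t) = a/(a + d) × [1 − exp(−(a + d)t)]
- Full follow-up: (1 − s)·G(h, T) + s·G(HR·h, T)
- Stopped patients censored c months after day 112: the full-follow-up value at c, plus S(c)·G(h, T − c), where S(c) is the proportion alive and AML-free at c.

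The largest gap is at h = 0.05, s = 50%, HR = 3, M = 9 (d = 0.0770). Full follow-up gives ½(0.257 + 0.561) = 40.9%.

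| Stopped patients censored at | Estimate | Gap among those alive and AML-free at day 112 | Upper limit from treatment start (gap × 0.753) |
|---|---|---|---|
| day 112 | 25.7% | 15.2 points | 11.4 points |
| day 149 | 29.7% | 11.2 points | 8.4 points |
| day 172 | 31.7% | 9.2 points | 6.9 points |

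The last column is an upper limit because 0.753 is the proportion alive at day 112, and fewer are also AML-free. With h = 0.03 and censoring at day 149, the conditional figures are 25.2% against 17.3% (M = 6) and 28.5% against 19.3% (M = 9).

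Death hazards matter too. Suppose stopped patients have a median survival of 4 months and the others 9 (s = 50%, censoring at day 149). With HR 1 and h = 0.03, full follow-up gives 14.3% and the censored estimate 15.7%, which is 1.4 points too high. With HR 3 and h = 0.05, the understatement falls from 11.2 to 6.2 points.

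A separate simulation counted from treatment start. It assumed 10-30% responders, an AML hazard of 0.02 per month in responders, median times to death of 8 months (non-responders) and 14 months (responders), and non-responders observed to 3.7 months plus 1. True against estimated 12-month incidence was 13.8-14.3% against 14.6-14.8% at HR 1, 22-24% against 19-20% at HR 2, and 29-32% against 23-25% at HR 3. About 45-54% of transformations within 30 months were observed.

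**The case against.** **Silence is not a prohibition.** Section 7.4 says REDCap will hold all efficacy data, and the case report form is not shown. Some transformations will be caught: AML that itself ends treatment as progression may be seen at an end-of-treatment marrow, and others may surface in the 28- to 30-day tail. This stands as a limit. It does not help patients stopped short of AML, because no section directs anyone to ask about AML at the 3-monthly contact.

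**Section 5.2.2 lets stable disease continue.** It allows patients with stable disease at the end of Cycle 2 to continue indefinitely. Sections 5.7.4 and 4.3, however, give up to four cycles to respond and then require a stop, and stable disease is not among the responses that avoid it.

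**Stronger readings that a reader might infer.** The documents do not support these:

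- *AML observation stops on the last day of treatment.* There is a tail of about 37 to 60 days, though it has no AML assessment assigned to it.
- *The plan censors patients at treatment stop.* It states no AML censoring rule; censoring near that point is an inference.
- *The bias must be an understatement, or is nil when AML hazards are equal.* Its direction depends on death hazards as well.
- *The 45 to 55 patients alive at day 149 are lost to AML observation.* That count includes responders still being observed.
- *An 11- or 15-point error applies to the whole trial.* Those figures are conditional on being alive and AML-free at day 112.

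**Weight.** This is an untested secondary endpoint in a single-arm exploratory study. That is fair, and it sets the priority of the point.

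**Conclusion.** The point holds. Following the plan as written, planned AML observation ends shortly after treatment, and when it ends depends on response. What rests on the documents is the absence of AML status from post-treatment collection, the stopping rules, and the window of about day 149 to 172 (day 205 to 228 with azacitidine from Cycle 3). On the plan's own survival assumptions, more than half of all patients are alive at day 172.

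The size and direction of the bias rest on assumptions. If stopped patients transform faster, the largest understatement over the assumed range is about 9 to 15 points among patients alive and AML-free at day 112, and no more than about 7 to 11 points from treatment start. If AML hazards are equal but stopped patients die faster, incidence is slightly overstated.

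A reader might take this as a threat to the primary endpoint. It is not, because survival is collected until death or loss to follow-up. It should be corrected because the endpoint cannot otherwise be interpreted much beyond the treatment period.

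**What to change.** **Section 5.5.** At each existing 3-monthly survival contact, record whether AML has been diagnosed and the date, whatever the reason for stopping treatment and for as long as survival is collected. State the blast threshold that counts as transformation. Patients with 20-30% blasts are eligible at entry (Section 4.1), so a 20% threshold would class them as AML at baseline.

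**Section 8.** Analyse time to AML transformation from start of treatment as cumulative incidence, with death without AML as a competing event. Censor at the last contact with known AML status, not at treatment stop.

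**Cost.** One data item at a contact that already takes place, and a few sentences in two sections. No extra visits, marrows or patients. The downside is that off-treatment AML dates will come from clinical records rather than scheduled marrows, so on- and off-treatment events should be reported separately.
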